4.3.1.7. Corticosteroid Taper (LN Cohort Only)

A corticosteroid taper will commence at Week 2 (Day 15). From Weeks 12 to 26, the target dose is 7.5 mg/day. Following Week 26, participants may remain on 7.5 mg/day or continue to taper at the clinical discretion of the Investigator until Week 46. From Weeks 46 to 50, the dose of corticosteroids must not be changed.

The percentage of participants receiving \leq 7.5 mg/day will be summarized at Weeks 12, 26, and 50 by treatment group by calculating the point estimate and 2-sided 95% CI based on exact confidence limits using the Clopper-Pearson method.

4.3.1.8. Renal Flare (LN Cohort Only)

Renal flare is determined in the opinion of the Investigator in addition to the criteria outlined below and will be recorded on the Renal Flare eCRF:

- For participants who achieve CRR, a renal flare is the reproducible recurrence of proteinuria $\geq 1~g/g$
- For all other participants, a renal flare is either of the following:
 - Reproducible increase of serum creatinine > 25% higher than baseline or above the upper limit of normal, plus any one of the following:
 - Reproducible proteinuria $\geq 75\%$ higher than baseline
 - Worsening active urinary sediment compared to baseline as defined by an increase of ≥ 5 red blood cells (RBC)/high power field (hpf) or new RBC casts (based on local laboratory results from at least 2 samples)
 - Kidney biopsy demonstrating LN Class III or IV activity that was conducted since the biopsy used for eligibility
 - Reproducible doubling of the UPCR from a 24-hour urine collection compared with the lowest previous value obtained after the first dose of study intervention

Reproducibility of proteinuria requires that UPCR from a morning spot urine collection be confirmed by a central laboratory UPCR based on 24-hour urine collected within 2 weeks.

Reproducibility of serum creatinine requires 2 blood tests within a 2-week period.

The percentage of participants meeting the criteria for renal flare through Week 50 will be summarized by treatment group by calculating the point estimate and 2-sided 95% CI based on exact confidence limits using the Clopper-Pearson method.

4.3.1.9. Extrarenal SLE Flare (LN Cohort Only)

Extrarenal SLE flare is defined as an increase in Systemic Lupus Erythematosus Disease Activity Index Safety of Estrogen in Lupus Erythematosus National Assessment Modification (SLEDAI-2K SELENA Modification) ≥ 4 points that is not accounted for by proteinuria, hematuria, urinary cellular casts, hypocomplementemia, or an increase in anti-double-stranded DNA (anti-dsDNA) antibody level and all instances are recorded on the Extrarenal SLE Flare eCRF.

The trajectory of SLEDAI-2K SELENA Modification score over time will be visually presented by plotting the mean values at each time point by treatment group.

The percentage of participants meeting the criteria for extrarenal SLE flare and severe extrarenal SLE flare through Week 50 will be summarized by treatment group by calculating the point estimate and 2-sided 95% CI, based on exact confidence limits using the Clopper-Pearson method.

4.3.1.10. Treatment Failure (LN Cohort Only)

Treatment Failure is defined as the receipt of additional standard of care therapy at any time up during the study for protocol-defined renal flare, severe extrarenal SLE flare, or suboptimal response as recorded on the Additional Standard of Care Therapy eCRF.

Increase in corticosteroids for extrarenal SLE flare not meeting the protocol definition of severe extrarenal SLE flare, renal flare not meeting protocol definition for renal flare, lack of response not meeting the protocol definition of suboptimal response, other medical conditions, or surgery limited to \leq 14 days duration are **not** included in treatment failure.

Participants who meet the criteria for treatment failure may continue to receive the study intervention and stay in the study. If a participant has 2 Treatment Failures, study intervention discontinuation should be considered. If a calcineurin inhibitor (CNI) is used for additional standard of care therapy, study intervention will need to be discontinued 3 days prior to CNI administration.

The percentage of participants meeting the criteria for treatment failure through Week 50 will be summarized by treatment group by calculating the point estimate and 2-sided 95% CI based on exact confidence limits using the Clopper-Pearson method.

4.3.1.11. Suboptimal Response (LN Cohort Only)

For the LN cohort, a suboptimal response is determined in the opinion of the Investigator in addition to the following criteria after the Week 26 Visit:

• Reproducible proteinuria ≤ 25% decreased compared to baseline based on UPCR on a 24-hour urine collection performed by central laboratory

Reproducibility of proteinuria requires that UPCR from a morning spot urine collection be confirmed by a central laboratory UPCR based on 24-hour urine collected within 2 weeks.

Participants with suboptimal response will stay in the study and continue to receive study intervention. Intensification of current standard of care or introduction of new immunosuppressive therapies are allowed per the clinical discretion of the Investigator in conversation with the Medical Monitor and will be considered additional standard of care therapy. Participants with suboptimal response will be included as treatment failure.

The percentage of participants meeting the criteria for suboptimal response will be summarized through Week 50 by treatment group by calculating the point estimate and 2-sided 95% CI based on exact confidence limits using the Clopper-Pearson method.

4.3.1.12. Serum Albumin (LN Cohort Only)

Serum albumin will be summarized at baseline and at Weeks 26 and 50 by treatment group using descriptive statistics as defined in Section 4.1 for the observed value as well as the change from baseline.

The trajectory of serum albumin over time will be visually presented by plotting the mean values at each time point by treatment group.

4.3.1.13. Partial Remission (IgAN Cohort Only)

For the IgAN cohort, partial remission will be defined as mean proteinuria < 1 g/24 hours based on 2 valid 24-hour urine collections obtained within 2 weeks prior to the study visit (Week 26 or 50).

The percentage of participants meeting the criteria for partial remission will be summarized at Weeks 26 and 50 by treatment group by calculating the point estimate and 2-sided 95% CI based on exact confidence limits using the Clopper-Pearson method.

Participants who discontinue treatment prior to the endpoint will be treated as failure to meet partial remission criteria and considered nonresponders.

A bar chart will also be provided displaying the proportion of participants meeting the criteria for partial remission at Weeks 26 and 50 by treatment group.

4.3.2. Sensitivity Analysis for Key Secondary Endpoints Due to Dosing Pause

4.3.2.1. Percentage Change in Proteinuria from Baseline to Week 50 (Both Cohorts)

Two sensitivity analyses will be used to assess the impact of dosing pause.

The endpoint will be analyzed in the same manner as described in Section 4.3.1.1, except that dosing pause would be regarded as intercurrent event, in which the analysis is similar to that of treatment discontinuation.

The endpoint will also be analyzed in the same manner as described in Section 4.3.1.1, except that only the participants in the population of no impact by dosing pause are included.

4.3.2.2. Reduction in Proteinuria at Weeks 26 and 50 Compared to Baseline (Both Cohorts)

The endpoint will also be analyzed in the same manner as described in Section 4.3.1.2, except that only participants in the population of no impact by dosing pause are included.

4.3.2.3. Change from Baseline in eGFR at Weeks 26 and 50 (Both Cohorts)

Two sensitivity analysis will be used to assess the impact of dosing pause.

The endpoint will be analyzed in the same manner as described in Section 4.3.1.3, except that dosing pause would be regarded as intercurrent event, in which the analysis is similar to that of treatment discontinuation.

The endpoint will also be analyzed in the same manner as described in Section 4.3.1.3, except that only the participants in the population of no impact by dosing pause are included.

4.3.2.4. Complete Renal Response (LN Cohort Only)

The endpoint will also be analyzed in the same manner as described in Section 4.3.1.4, except that only the participants in the population of no impact by dosing pause are included.

4.3.2.5. Partial Renal Response (LN Cohort Only)

The endpoint will also be analyzed in the same manner as described in Section 4.3.1.5, except that only the participants in the population of no impact by dosing pause are included.

4.3.2.6. Partial Remission (IgAN Cohort Only)

The endpoint will also be analyzed in the same manner as described in Section 4.3.1.13, except that only the participants in the population of no impact by dosing pause are included.

4.4. Exploratory Endpoint Analysis

The exploratory analyses will be based on the FAS. These analyses will be descriptive in nature and no adjustment for multiplicity will be performed. In addition, there will be no imputation for missing data or data collected on or after the receipt of additional standard-of-care therapy (LN cohort only) or treatment discontinuation unless otherwise specified.

Summary statistics will be computed and displayed by treatment group and by visit, where applicable. Descriptive statistics for continuous variables will minimally include the number of participants, mean, SD, minimum, median, and maximum. For categorical variables, frequencies and percentages will be presented.

The analyses for participants in the LN cohort and participants in the IgAN cohort will be conducted and reported separately. Participants in each disease-specific cohort will be analyzed as randomized, regardless of actual treatment received.

4.4.1. Percentage Change in Proteinuria from Baseline to Weeks 102 and 154 (Both Cohorts)

The analysis will be performed at Weeks 102 and 154 using the same approach as defined in Section 4.3.1.1. Results will be presented for each treatment sequence group.

4.4.2. Change from Baseline in eGFR at Weeks 102 and 154 (Both Cohorts)

The analysis will be performed at Weeks 102 and 154 using the same approach as defined in Section 4.3.1.3. Results will be presented for each treatment sequence group.

4.4.3. Effect on Hematuria (Both Cohorts)

For both cohorts, the effect on hematuria will be measured by the following:

- RBC in urine from baseline to Weeks 26 and 50
- Participants achieving < 10 RBC/hpf

RBC in urine will be summarized at each time point by treatment group using frequency statistics for categorical variables. The percentage of participants with < 10 RBC will be summarized at each scheduled visit by calculating the point estimate and 2-sided 95% CI based on exact confidence limits using the Clopper-Pearson method.

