To assess the efficacy of ALXN2050 in	Percentage change in proteinuria from baseline to Week 102 and Week 154 (based on 24-hour urine collection[s])				
exploratory efficacy endpoints	Change from baseline in eGFR at Week 102 and Week 154				
	Effect on hematuria as measured by				
To evaluate the efficacy of ALXN2050 on hematuria in participants with LN or IgAN	 Absolute value and change from baseline in RBC in urine from baseline to Week 26 and Week 50 				
	Achieving < 10 RBC/hpf				
To assess quality of life based on participant-reported outcomes in participants	Change from baseline in SF-36 at Week 26 and Week 50				
with LN or IgAN based on treatment with ALXN2050	Change from baseline in EQ-5D-5L at Week 26 and Week 50				
To evaluate biomarkers such as complement, autoimmune, and renal in participants with LN or IgAN	Absolute values and change from baseline in levels of biomarkers in blood and urine over time				
Exploratory (LN Cohort Only)					
	Time to the first CRR or PRR (using spot UPCR)				
To assess the efficacy of ALXN2050 in exploratory efficacy endpoints	Meeting the criteria for Overall Renal Response (CRR or PRR) at Week 26 and Week 50				
	Time to the first occurrence of UPCR > 50% decrease from baseline (using spot UPCR)				
To assess quality of life based on participant-reported outcomes	Change from baseline in FACIT-Fatigue total score at Week 26 and Week 50				
To assess the efficacy of ALXN2050 in other exploratory endpoints	Histology changes from baseline to Week 50, if tissue is available				

Table 7: Mapping Objectives to Endpoints

Objectives	Endpoints
	Absolute values and change from baseline in anti- dsDNA and anti-C1q antibodies at Week 26 and Week 50
Exploratory (IgAN Cohort Only)	
To assess the efficacy of ALXN2050 in exploratory efficacy endpoints	Slope of eGFR computed from baseline to Week 26 and Week 50

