Proteinuria is further justified as an endpoint in this Phase 2 study because ALXN2050 has potential for anti-inflammatory effects that may be demonstrated through changes in proteinuria. Proteinuria may also result from irreversible scarring of renal tissue. Therefore, the presence of potentially reversible and active inflammatory kidney disease is ensured by requiring hematuria in participants with IgAN, and active Class III or IV LN on kidney biopsy in participants with LN. Additionally, relatively preserved renal function with an eGFR of > 30 mL/min/1.73 m² is required for both disease cohorts. Finally, although treatment response in patients with LN is traditionally defined by stratification into complete and partial response, there is no consensus definition across guidelines, and proteinuria is the most important clinical variable used to define response (Parikh, 2016). In fact, a retrospective analysis of 1-year clinical response metrics from the Euro Lupus Nephritis Trial demonstrated proteinuria < 800 mg/day at 1 year to be the best predictor of good long-term renal outcome. The addition of serum creatinine level and microscopic hematuria did not improve the prediction model (Parikh, 2020).

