5.1.3. Inclusion Criteria Specific for IgAN Cohort

- Established diagnosis of primary IgAN based on kidney biopsy (Section 10.9) obtained any time prior to or during the Screening Period.
- 13. Mean proteinuria ≥ 1 g/day on 2 complete and valid 24-hour urine collections during the Screening Period.
- 14. For participants with a kidney biopsy performed > 1 year prior to Screening that was used for eligibility:
 - Presence of hematuria as defined by a positive result for blood on urine dipstick or ≥ 10 red blood cells (RBCs)/high-power field (hpf) microscopy on urine sediment (documented by the local laboratory) during Screening Period. Presence of hematuria documented by the central laboratory may also be acceptable.
- 15. Compliance with stable and optimal dose of RAS inhibitor treatment including maximum allowed or tolerated ACE inhibitor and/or ARB dose for ≥ 3 months prior to Screening with no expected change in dose during the Blinded Treatment Periods (through Week 50) (participants with established intolerance to RAS inhibitors may be included).
- Controlled and stable blood pressure (defined as < 140/90 mmHg) over the past 3 months prior to randomization.

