8.1.4. Hematuria (Both Cohorts)

For participants in both disease cohorts, hematuria from spot urine samples will be evaluated to assess the effect of study intervention on disease course. The degree of hematuria will be assessed by examination of the spun urine sediment by microscopy (RBC/hpf).

Single void collections for random spot urine sample for hematuria evaluation should be collected. If the Investigator determines that the hematuria is transient due to menses in women or exercise, the sample may need to be repeated.

Random spot urine samples for hematuria measurement will be collected throughout the study as outlined in the SoA (Section 1.3) and will be analyzed by a central laboratory. Samples should be collected prior to study intervention administration, if applicable.

The local hematuria evaluation by microscopy or urinary dipstick may be used to determine eligibility for the study at Screening for participants with IgAN, if diagnostic biopsy is > 1 year old.

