8.2.4.3. Routine Urinalysis and Urine Sediment

Urine samples will be collected at times specified in the SoA and analyzed for the parameters listed in Section 10.2. A microscopic examination of urine samples will be performed if the results of the macroscopic analysis are abnormal. Samples will be obtained from a morning void prior to dosing.

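### The hematuria responder percentage in SAP 4.4.3 has no baseline condition, so participants who enter below 10 RBC/hpf count as having achieved the outcome

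*SAP*

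**What the plan says.** **Objective.** Protocol Section 3 lists, as exploratory for both cohorts: "To evaluate the efficacy of ALXN2050 on hematuria in participants with LN or IgAN". It gives two measures: urine RBC as absolute value and change from baseline, and reaching fewer than 10 RBC/hpf.

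**Analysis.** SAP 4.4.3 names the second measure "Participants achieving < 10 RBC/hpf" and specifies: "The percentage of participants with < 10 RBC will be summarized at each scheduled visit", with a Clopper-Pearson 95% CI. SAP 4.4 sets the population: "The exploratory analyses will be based on the FAS". SAP 4.8 records that urine RBC arrives from the laboratory as categories, so the continuous analysis is replaced by category frequencies at each time point.

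**Entry.** The LN inclusion criteria (Protocol 5.1.2) do not mention hematuria. IgAN criterion 14 (Protocol 5.1.3) is limited by its opening words: "For participants with a kidney biopsy performed > 1 year prior to Screening". Within that group either a positive dipstick for blood or at least 10 RBC/hpf qualifies. Protocol 8.1.4 repeats the biopsy-age condition. Protocol 4.2.1 omits it and says that potentially reversible, active disease "is ensured by requiring hematuria in participants with IgAN".

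**Microscopy.** Protocol 8.2.4.3 says: "A microscopic examination of urine samples will be performed if the results of the macroscopic analysis are abnormal". Protocol 8.1.4, by contrast, grades hematuria by sediment microscopy, and Table 13 lists RBC/hpf, both without that condition.

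**The concern.** The word achieving implies a move from at or above 10 RBC/hpf to below it. The planned percentage instead counts everyone who is below 10 at the visit, including those who were never above it. Such participants have no hematuria to clear. They raise the percentage in every arm and pull the arms together. A high percentage could then reflect who was enrolled rather than what the drug did, and a real effect on hematuria would look smaller than it is. Because the change-from-baseline measure became categorical, nothing else in the hematuria analysis shows change within a participant.

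**Working it through.** The documents state no rate or power for this endpoint, so there is no planned figure to reproduce. The check sets the entry criteria against the denominator and then sizes the effect.

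**1. Who can be below 10 RBC/hpf at baseline**

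| Group | Hematuria required at entry? | Can be < 10 RBC/hpf at baseline? |
|---|---|---|
| LN | No (Protocol 5.1.2) | Yes |
| IgAN, biopsy within 1 year | No (criterion 14 does not apply) | Yes |
| IgAN, biopsy > 1 year old | Yes, but a positive dipstick suffices | Yes |

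All three groups are in the FAS denominator.

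**2. Size of the dilution**

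Let q be the share below 10 at baseline who stay below 10, and p the clearance rate among the others. Then:

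- percentage reported in an arm = q + (1 - q) × p
- difference between arms = (1 - q) × (p_active - p_placebo)

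The documents give neither q nor p. Assume p_placebo = 30% and p_active = 60%, a true difference of 30 points:

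| q (assumed) | Placebo | Active | Difference |
|---|---|---|---|
| 0.1 | 0.1 + 0.9 × 0.3 = 37% | 0.1 + 0.9 × 0.6 = 64% | 27 points |
| 0.5 | 0.5 + 0.5 × 0.3 = 65% | 0.5 + 0.5 × 0.6 = 80% | 15 points |
| 0.6 | 0.6 + 0.4 × 0.3 = 72% | 0.6 + 0.4 × 0.6 = 84% | 12 points |

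**3. Floor with no clearance at all**

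With p = 0 the arm still reports q. At q = 0.5 that is 12/24 = 50% (95% CI 29% to 71%) in an IgAN arm of 24, and 15/30 = 50% (31% to 69%) in an LN arm of 30.

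**4. Whether another planned output fills the gap**

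Category frequencies by time point show each arm's distribution at baseline and at each visit, which is a net change only. Take a hypothetical arm of 24 with 12 below 10 at baseline and 16 below 10 at Week 26:

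- 4 resolved and 0 new: 12 + 4 - 0 = 16, so resolution is 4/12 = 33%.
- 8 resolved and 4 new: 12 + 8 - 4 = 16, so resolution is 8/12 = 67%.

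The frequency tables are the same in both cases. The laboratory shift tables in SAP 4.5.3.1 use normal-range classes in the Safety Set, not the 10 RBC/hpf threshold. SAP 4.4.11 plans shift tables for histology, but 4.4.3 plans none for hematuria.

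**5. Which visits are affected**

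In LN the between-arm argument applies at Weeks 26 and 50. In IgAN it applies at Week 26 only, because the placebo group then switches to ALXN2050.

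**The case against.** The strongest reply is that little depends on this measure. It is exploratory and descriptive, SAP 4.4.3 plans percentages per arm with no test and no between-arm estimate, and no stated decision uses it. All of that stands, and it limits the importance of the point.

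Second, each arm's baseline RBC distribution is already planned, so an attentive reader could see the dilution. That stands for the distribution, but not for who converted (step 4).

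Third, the FAS percentage is a legitimate summary. It keeps the randomized groups intact, and it captures any benefit in preventing new hematuria, which a restricted denominator would lose. This also stands, and it is the reason to add to the summary rather than replace it.

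Fourth, q may be small. Protocol 2.2.4 says IgAN patients initially present with hematuria, and LN participants need active Class III or IV disease. At q = 0.1 the loss is only 3 points.

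A reader might also draw three stronger inferences that the documents do not support:

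- **That complete responders lose their RBC/hpf value when hematuria clears, because 8.2.4.3 makes microscopy conditional.** Protocol 8.1.4 and Table 13 call for sediment RBC/hpf without that condition, and the Schedule of Activities lists urine sediment at every scheduled clinic visit through Week 50. Even if 8.2.4.3 governed, the trigger is any abnormality on a panel that includes protein. Everyone enters with proteinuria of at least 1 g/g or 1 g/day, and the reductions assumed for the 180 mg group are 60% (LN) and 45% (IgAN). Clearing blood alone would not stop the microscopy. The wording conflict is real, since the schedule row cites 8.2.4.3, but it needs only a clarification.
- **That participants were enrolled against the intended criteria.** The sentence in 4.2.1 is rationale. The operative text in criterion 14 and 8.1.4 is consistent.
- **That a baseline-hematuria subgroup for the primary endpoint is needed.** The SAP already reports time from biopsy, and it splits the MEST-C and C3-staining subgroup summaries at a biopsy age of 1 year where feasible. A further subgroup is optional.

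**Conclusion.** The point holds as a modest, inexpensive improvement. As planned, the percentage mixes participants whose hematuria resolved with participants who never had 10 RBC/hpf or more, and no planned output separates them at that threshold. The between-arm difference is multiplied by (1 - q): a true 30 points becomes 27, 15 or 12 at q = 0.1, 0.5 or 0.6. These values of q are assumptions, as are the 30% and 60% clearance rates. The formula also assumes that nobody who starts below 10 rises above it. The actual q will be known from the baseline data. The primary endpoint, its power and the safety analyses are not touched.

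**What to change.** In SAP 4.4.3 keep the FAS percentage and add:

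- **(a)** the percentage reaching < 10 RBC/hpf among participants with >= 10 RBC/hpf at baseline, and the percentage with new hematuria (>= 10) among the rest, by arm with exact CIs;
- **(b)** a shift table of RBC categories by arm, from baseline to Week 26 and from baseline to Week 50. For IgAN at Week 50, present it by treatment sequence and state which baseline is used.

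Two wording clarifications go with this. Reconcile Protocol 8.2.4.3 with 8.1.4, Table 13 and the Schedule of Activities on whether sediment is read at every scheduled visit. Align the hematuria sentence in 4.2.1 with criterion 14.

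**Cost.** The added analyses use data already scheduled, with no new visits or samples. The downside is precision in (a). If half of an IgAN arm of 24 is below 10 at baseline, 4/12 has a 95% CI of 10% to 65%, while the FAS figure (12 + 4)/24 = 16/24 has 45% to 84%. In an LN arm of 30, 4/15 gives 8% to 55%, against 44% to 80% for (15 + 4)/30 = 19/30. Reporting both keeps the FAS summary and answers the question the objective asks.
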